### Subjects with T2DM

Subjects with T2DM will continue their usual treatment, except for subjects taking sulfonylurea (SU) or insulin. These subjects may be at an increased risk of hypoglycemia due to the combination of the SU or insulin and weight loss, with or without consequent treatment with LIK066 in Epoch 3. Therefore:

- The dose of SUs for subjects with T2DM (see [Section 3.1.2 & Section 5.3](#)) using such medication (either as monotherapy or in combination with other oral anti-diabetic drugs (OADs)) must be reduced by 50 %, or as close to 50 % as possible based on dose options available locally. In case of persistent deterioration in glycemic control, the concomitant background OAD should be initially escalated to the maximal approved dose, followed by addition of rescue medication when required (see [Section 5.5.6](#)). To limit the number of subjects with early deterioration of glycemic control who would meet the FPG rescue

criteria early after randomization (see [Section 5.5.6](#)), an FPG randomization criterion is included in [Section 4.2](#).

- For subjects on insulin, initial dose reduction of the total daily insulin dose by 10 % or more may be considered at investigator's discretion based on subject's total daily dose and glycemic control. In case of deterioration in glycemic control, insulin can be up-titrated (see [Section 5.5.6](#)).

### **3.1.2    Epoch 3 (treatment)**

After the run-in Epoch 2, eligible subjects will be randomized in the ratio of 1:1:1:2:1:1:1:2:2 to one of the following regimes at Visit 201 (randomization):

- 2.5 mg qd LIK066.
- 10 mg qd LIK066.
- 50 mg qd LIK066.
- 150 mg qd LIK066.
- 2.5 mg bid LIK066.
- 5 mg bid LIK066.
- 25 mg bid LIK066.
- 50 mg bid LIK066.
- Placebo.

At Visit 201, subjects will be randomized simultaneously to one of the nine Epoch 3 treatment schedules and to the subsequent treatment group/arm in Epoch 4 as follows:

- Patients receiving one of the four LIK066 doses in the qd regimen in Epoch 3 will receive 25 mg qd in Epoch 4.
- Patients receiving one of the four LIK066 doses in the bid regimen in Epoch 3 will receive 35 mg qd in Epoch 4.
- Patients receiving placebo in Epoch 3 will either receive in a 1:1 ratio 25 mg qd or placebo in Epoch 4.

At randomization, subjects will be stratified according to their glycemic status at screening using the following criteria (see also [Section 5.3](#)):

[figure not shown]
- Normoglycemic: no prior clinical diagnosis of T2DM, FPG < 5.6 mM (100 mg/dL) and HbA1c < 5.7 % at Visit 1 (screening).
- T2DM: prior diagnosis of T2DM, or subjects without prior diagnosis of T2DM with HbA1c ≥ 6.5 % and FPG ≥ 7.0 mmol/L (126 mg/dL) at Visit 1 (screening).
- Dysglycemic: all subjects not meeting criteria for normoglycemic or T2DM at Visit 1 (screening).

Following randomization, subjects will attend study visits in Epoch 3 (24 weeks) for assessment of efficacy, tolerability and safety parameters as defined in [Table 6-1](#). During Epoch 3, subjects will take the study medication as described in [Section 5.5.4](#).

The doses of antidiabetic and antihypertensive medications should be adjusted in patients who, according to the investigator, could be at a safety risk (e.g. repetitive or severe hypoglycemia, symptoms and signs of volume depletion, etc.).

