### 3.2 Rationale for study design

The study is designed as a standard placebo-controlled, parallel-group study to obtain efficacy, tolerability and safety data in an unbiased fashion and determine the dose-response

characteristics of the investigated drug. A single-blind placebo run-in period is included to facilitate the implementation of lifestyle measures, as well as assess the compliance with study treatment. Twenty-four weeks of treatment in Epoch 3 are considered sufficient to reach sub-maximal or maximal weight loss. The last 24 weeks of the study will provide information about the effect of two doses of LIK066 on weight, and also LIK066 safety and tolerability over a longer period (48 weeks). In addition to collection of trough PK samples in all subjects, PK sampling will be performed in a subset of subjects to enable characterization of the PK of LIK066 in the studied population and, if possible, from all tested doses and regimens in the study (see [Section 6.6.3](#)).

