### **5.2 Treatment arms**

All subjects entering Epoch 2 (run-in) will receive placebo.

At Visit 201 (randomization), subjects eligible for randomization will be assigned 1:1:1:2:1:1:1:2:2 to one of the following treatment arms in Epoch 3 (see [Section 3.1.2](#)):

- 2.5 mg qd LIK066 (approx. 36 subjects).
- 10 mg qd LIK066 (approx. 36 subjects).
- 50 mg qd LIK066 (approx. 36 subjects).
- 150 mg qd LIK066 (approx. 72 subjects).
- 2.5 mg bid LIK066 (approx. 36 subjects).
- 5 mg bid LIK066 (approx. 36 subjects).
- 25 mg bid LIK066 (approx. 36 subjects).
- 50 mg bid LIK066 (approx. 72 subjects).

- Placebo (approx. 72 subjects).

At the end of Epoch 3, subjects from each of the four qd arms will enter Epoch 4 and will receive 25 mg qd LIK066. Subjects from each of the four bid arms in Epoch 3 will receive 35 mg qd LIK066 in Epoch 4.

The subjects from the Epoch 3 placebo arm will receive placebo or 25 mg qd LIK066 in Epoch 4 in a 1:1 fashion (see [Section 3.1.3](#)).

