## 9.8 Sample size calculation

The study planned to randomize approximately 432 subjects in total, allocated in the ratio of 1:1:1:1:1:2:1:1:1:2 to the following ten Epoch 3/Epoch 4 treatment groups:

1. placebo/placebo
2. placebo/LIK066 25 mg qd
3. LIK066 2.5 mg qd/25 mg qd
4. LIK066 10 mg qd/25 mg qd
5. LIK066 50 mg qd/25 mg qd
6. LIK066 150 mg qd/25 mg qd
7. LIK066 2.5 mg bid/35 mg qd
8. LIK066 5 mg bid/35 mg qd
9. LIK066 25 mg bid/35 mg qd
10. LIK066 50 mg bid/35 mg qd

This randomization scheme implies that the Epoch 3 treatment and Epoch 4 treatment for a specific subject is determined simultaneously at randomization visit. The randomization will be stratified by subjects' glycemic status at screening: normoglycemic, dysglycemic and T2DM (see [Section 3.1.2](#)).

As the dose-response assessment is conducted in qd and bid regimens separately (while an overall family-wise type I error is controlled at a one-sided significance level of 2.5 %), power calculation was done for testing dose-response signal by regimen as well. [Table 9-2](#) summarizes the average power and the lowest power across the candidate dose response shapes in [Figure 9-1](#) by regimen, under different scenarios with the assumptions on effect size of body weight loss (percent change from BL) for the dose of maximum effect, and the related standard deviations.

Note that a dose-response signal is detected (ie the primary objective is met) as long as either of the dose-response signals for the two regimens is detected. Therefore, the overall study power is at least the maximum of the powers between two regimens for each scenario considered.

It was assumed that the effect of losses to follow-up is equivalent to effectively having 15 % fewer subjects than randomized, even if the multiple imputation approach used to handle missing values should be able to recover some information for such subjects.

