2.1.1 General definitions

Baseline (Week 0) for Week 24 analysis and overall analysis including both Epoch 3 and Epoch 4 data will be defined as the last measurement before or at the randomization visit. Baseline for End of study analysis including Epoch 4 data only will be defined as the last measurement in Epoch 3.

The first day of administration of randomized study treatment (first dose) is defined as Day 1 for the study. If the date of first administration is missing, then randomization date will be used as Day 1.

All other study days will be labeled relative to Day 1. For event dates on or after Day 1, study day for a particular event date is calculated as [Date of event] – [Date of first dose] + 1. For the dates before Day 1, study day for an event date is calculated as [Date of event] – [Date of first dose]. Duration of an event will be calculated as [Event end date] – [Event start date] + 1. The descriptor “Day 0” will not be used.

For Week 24 analysis, the treatment groups presented are:

- LIK066 2.5 mg qd
- LIK066 10 mg qd
- LIK066 50 mg qd
- LIK066 150 mg qd
- LIK066 2.5 mg bid
- LIK066 5 mg bid
- LIK066 25 mg bid
- LIK066 50 mg bid
- Placebo
- Total (if applicable)

For End of study analysis, unless specified otherwise, the following treatment grouping strategy will be used, expressed as per the Epoch 3 treatment/Epoch 4 treatments a subject is assigned to at randomization:

- LIK066 qd any dose/LIK066 25 mg qd, shortened as LIK066 qd/LIK066 25 mg qd
- LIK066 bid any dose/LIK066 35 mg qd, shortened as LIK066 bid/LIK066 35 mg qd
- Placebo/LIK066 25 mg qd
- Placebo/placebo, shortened as Placebo
- Total (if applicable)

For End of study AE listings, the 10 randomized treatments will be used, as shown in Section 1.1 study design, along with the additional two pooled groups:

- LIK066 qd any dose/LIK066 25 mg qd, shortened as LIK066 qd/LIK066 25 mg qd
- LIK066 bid any dose/LIK066 35 mg qd, shortened as LIK066 bid/LIK066 35 mg qd
- Total (if applicable)

For overall analysis including both Epoch 3 and Epoch 4 treatment, the 10 randomized treatment grouping strategy will be used, as shown in Section 1.1 Study design.

For the Week 24 analyses, data collected up to the end date of Epoch 3 will be included. For AEs and concomitant medications, this means that events with start dates prior to the end of Epoch 3 dates are included.

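### The Week 24–48 efficacy model pools all Epoch 3 doses of a regimen, so the active-origin means depend on the Epoch 3 dose mix, and 25 vs 35 mg cannot be separated from qd vs bid history

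*Protocol*

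**What the plan says.** Protocol 3.1.2 fixes the Epoch 4 treatment at Visit 201 by three rules. All four qd arms move to 25 mg qd. For the other regimen the text reads: "Patients receiving one of the four LIK066 doses in the bid regimen in Epoch 3 will receive 35 mg qd in Epoch 4". Only the placebo arm is split: half of it goes to 25 mg qd and half stays on placebo.

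Protocol 3.2 gives the efficacy purpose: "The last 24 weeks of the study will provide information about the effect of two doses of LIK066 on weight". Protocol 3.1.3 describes the two active groups as showing longer-term results of LIK066 after earlier LIK066 treatment. Protocol 3.3 expects the Epoch 4 doses to maintain the weight loss of Epoch 3 well.

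For the End of study analysis, SAP 2.1.1 forms four groups. One is "LIK066 qd any dose/LIK066 25 mg qd, shortened as LIK066 qd/LIK066 25 mg qd", and the bid arms are pooled in the same way. Placebo/25 mg and placebo/placebo stay separate. The baseline is the last Epoch 3 measurement. The repeated-measures model in SAP 2.7.2.2 has treatment (these groups), visit, pooled center or region, treatment by visit, baseline and baseline by visit. Its contrasts are LIK066 vs placebo on change from Week 24 to Week 48.

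SAP 2.1.1 keeps the ten sequences for overall analyses of Epochs 3 and 4. The outputs that name them concern disposition, exposure and adverse events (SAP 2.3.2, 2.4.1, 2.8.1). None is an efficacy output.

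**The concern.** A subject's change after Week 24 depends on the dose left behind as well as the dose taken up. The plan's alternative hypotheses say that weight falls as dose rises, so subjects moving up would be expected to lose more weight and subjects moving down to regain some. Averaging them in proportions set by the allocation ratio gives a number that belongs to that mixture and not to 25 mg or 35 mg.

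Two readings are at stake. A pooled change near zero could be reported as maintenance, which Protocol 3.3 expects, although it may be an average of further loss and regain. A difference between the 25 mg and 35 mg groups could be read as a dose effect, although it is equally a difference in qd and bid history.

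The baseline covariate does not cure this. Two subjects with the same Week 24 weight may have reached it on different doses and face different dose changes.

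**Working it through.** **Allocation.** Protocol 9.8: "The study planned to randomize approximately 432 subjects in total", in the ratio "1:1:1:1:1:2:1:1:1:2 to the following ten Epoch 3/Epoch 4 treatment groups". The ratio sums to 12 units, so one unit is 432/12 = 36. This reproduces the arms of 36 and 72 in Protocol 5.2. The effective size also reproduces: 432 × 0.85 = 367.2, stated as 367. No sample size, power or precision is given for Epoch 4.

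**Direction of the dose change, by total daily dose.**

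| Epoch 4 group | Moves up | Moves down |
|---|---|---|
| 25 mg qd, n = 180 | 2.5 and 10 mg: 36 + 36 = 72 (40 %) | 50 and 150 mg: 36 + 72 = 108 (60 %) |
| 35 mg qd, n = 180 | 5 and 10 mg: 36 + 36 = 72 (40 %) | 50 and 100 mg: 36 + 72 = 108 (60 %) |

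No qd subject receives 35 mg, no bid subject receives 25 mg, and no placebo subject receives 35 mg.

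**Illustration with the plan's candidate shapes.** Assumptions, none stated in the documents for Epoch 4: a maximum effect of 5 % at the best studied dose; the same curve in total daily dose applies in Epoch 4; the effect reaches the new dose's level by Week 48; changes are net of placebo. Change = E(Epoch 3 dose) − E(Epoch 4 dose), with negative values meaning further loss.

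Worked case, Emax with ED50 = 50 mg:

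- qd: E(d) = 5 × [d/(50+d)] / [150/200]. E is 0.32, 1.11, 3.33 and 5.00 at 2.5, 10, 50 and 150 mg, and 2.22 at 25 mg. The changes are -1.90, -1.11, +1.11 and +2.78. Pooled: [36(-1.90) + 36(-1.11) + 36(1.11) + 72(2.78)]/180 = **+0.73**. A placebo subject switching to 25 mg changes by **-2.22**.
- With four equal qd arms, the same drug effect would give (-1.90 - 1.11 + 1.11 + 2.78)/4 = +0.22. The pooled figure moves with the allocation alone.
- bid: E is 0.68, 1.25, 3.75 and 5.00 at 5, 10, 50 and 100 mg/day, and 3.09 at 35 mg. The changes are -2.41, -1.84, +0.66 and +1.91. Pooled: [36(-2.41 - 1.84 + 0.66) + 72(1.91)]/180 = **+0.05**, against -3.09 from placebo.

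Across all six shapes for each regimen, in percentage points:

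| Epoch 4 dose | Moving up | Moving down | Pooled | From placebo |
|---|---|---|---|---|
| 25 mg qd | -0.1 to -1.7 | +0.6 to +3.6 | -0.3 to +2.1 | -0.1 to -4.3 |
| 35 mg qd | -0.6 to -3.0 | +0.3 to +3.3 | -0.8 to +1.7 | -0.6 to -4.6 (no such group exists) |

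The pooled change is positive, opposite to the effect from placebo, in five of six qd shapes and three of six bid shapes. SAP 2.7.2.2 models absolute weight change; the percentage scale here does not alter the argument.

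**Precision.** The 95 % half-width is 1.96 × SD × √(1/n1 + 1/n2), borrowing the SDs of 5.5 and 6.5 from Protocol Table 9-2 because none is given for Week 24–48 change.

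| Contrast with placebo/placebo (36) | SD 5.5 | SD 6.5 |
|---|---|---|
| Pooled group, 180 | 1.97 | 2.33 |
| One sequence, 72 | 2.20 | 2.60 |
| One sequence, 36 (including placebo/25 mg) | 2.54 | 3.00 |

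With 15 % losses, the last row becomes 2.76 and 3.26 (30.6 per group). For placebo/25 mg vs placebo/placebo at 36 each, two-sided 5 %, power is 97 % (SD 5.5) or 90 % (SD 6.5) for a 5-point difference, and 64 % or 50 % for 3 points.

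**The case against.** A reader might infer that Epoch 4 dose is completely aliased with Epoch 3 regimen, that every Epoch 4 group mixes upward and downward moves, and that Epoch 4 therefore says nothing about either dose. The documents do not support this. Placebo subjects are randomised 1:1 to 25 mg or placebo and analysed as two separate groups. They share the same Epoch 3 treatment, so their change from Week 24 compares 25 mg with placebo without a dose mixture. Two of the four analysis groups mix nothing.

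Further points in the plan's favour:

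- No 25 vs 35 mg test is planned. Protocol 3.2 promises information on two doses, not a comparison of them. This stands, but side-by-side results invite the comparison.
- The up and down counts use nominal milligrams. Protocol 3.3 places 10 and 50 mg qd, 72 of the 180 qd subjects, in nearly the same effect category as the Epoch 4 doses. This stands: opposite movement is not established for every subject. The clear moves that remain are still in both directions: 2.5 mg (36) up and 150 mg (72) down.
- An exactly flat pooled mean needs particular values. This also stands: zero lies inside both pooled ranges but is one outcome among many.
- The ten sequences are already used for overall analyses. This answers part of the point for exposure and adverse events, but no named efficacy output uses them. SAP 2.7.2.2 also does not carry over the change-from-baseline summaries and 48-week figures of Protocol 9.5.1.2.
- Epoch 4 efficacy is secondary, with no key secondary objective. This limits the weight of the point.

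**Conclusion.** The concern holds for the two active-origin groups. Among subjects on active drug in Epoch 3, Epoch 4 dose and Epoch 3 regimen coincide exactly (180 and 180). Each pooled group is 40 % up and 60 % down by total daily dose, and the model has no Epoch 3 dose term. The pooled Week 24–48 change and its contrast with placebo/placebo describe a mixture of sequences. They can be near zero or opposite in sign to the dose's effect from placebo. A 25 vs 35 mg difference cannot be separated from qd vs bid history, and 35 mg has no contrast free of prior active treatment.

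The counts follow directly from the documents. The sizes in points rest on the assumed 5 % maximum, an unchanged curve and a full response to the new dose by Week 48. They show what is possible and are not a forecast.

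For 25 mg, the placebo-origin contrast is sound but small and was not powered. The Week 24 primary analysis is not touched. This is a cheap improvement to a secondary analysis.

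**What to change.** In SAP 2.7.2.2:

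1. Also report body weight change from Week 24 to Week 48, and from baseline to Week 48, by the ten randomised sequences. Alternatively, add Epoch 3 dose as a factor within each pooled group.
2. Name placebo/25 mg vs placebo/placebo as the contrast for 25 mg.
3. State that the pooled active-origin means are not to be read alone as maintenance, and that 25 vs 35 mg is not estimable free of Epoch 3 regimen.

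The pooled groups can stay as a summary. The cost is programming, SAP text and wider intervals: about 2.5 to 3 points half-width for 36 vs 36, against about 2.0 to 2.3 for a pooled group vs placebo/placebo, before losses and with the Epoch 3 SDs. By-sequence results are therefore descriptive. No new subjects or data are needed. A different allocation to Epoch 4 is not proposed: it would split arms of 36 further, and allocation was fixed at Visit 201.

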### Figure 3-1 Study design

#### 3.1.3 Epoch 4

After completing the procedures required at the last study visit of Epoch 3 (Visit 299), subjects in active study drug Epoch 3 arms will be switched to receive either LIK066 25 mg qd or LIK066 35 mg qd for another 24 weeks (see [Figure 3-1](#)).

The Epoch 3 placebo arm subjects will either continue the placebo treatment regimen or switch to LIK066 25 mg qd in a 1:1 ratio.

Except for the placebo arm, the switch will result in 2 study groups, active drug 25 mg qd or 35 mg qd, in which longer-term safety, tolerability and efficacy of LIK066 following LIK066 treatment will be assessed. The rationale for the study design is presented in [Section 3.2](#).

The doses of antidiabetic and antihypertensive medications should be adjusted in patients who, according to the investigator, could be at a safety risk (e.g. repetitive or severe hypoglycemia, symptoms and signs of volume depletion, etc.).

#### 3.1.4 PK evaluation

PK sampling will be performed at visits indicated in [Table 6-1](#) (see also [Section 6.6.3](#)).

### 3.2 Rationale for study design

The study is designed as a standard placebo-controlled, parallel-group study to obtain efficacy, tolerability and safety data in an unbiased fashion and determine the dose-response

characteristics of the investigated drug. A single-blind placebo run-in period is included to facilitate the implementation of lifestyle measures, as well as assess the compliance with study treatment. Twenty-four weeks of treatment in Epoch 3 are considered sufficient to reach sub-maximal or maximal weight loss. The last 24 weeks of the study will provide information about the effect of two doses of LIK066 on weight, and also LIK066 safety and tolerability over a longer period (48 weeks). In addition to collection of trough PK samples in all subjects, PK sampling will be performed in a subset of subjects to enable characterization of the PK of LIK066 in the studied population and, if possible, from all tested doses and regimens in the study (see [Section 6.6.3](#)).

### **3.3 Rationale for dose/regimen, route of administration and duration of treatment**

PK data with oral intake of LIK066 showed a sufficiently long half-life (approximately 16h) to allow for once-daily LIK066 dosing. LIK066 150 mg qd was used in a Phase 1 study of 12 weeks duration, at a dose which is approximately 23 times below the safety margin for aneugenicity (see [Section 3.6](#)), and expected not to limit compliance due to GI effects. In this study, significant weight reduction of approximately 6 % vs placebo was observed, but it was commonly associated with diarrhea events, predominantly mild, at a frequency which reduced over time in most subjects. Therefore a dose of 150 mg qd is selected as the highest qd dose in the current study. Twice daily dosing will be explored to evaluate whether increased frequency of LIK066 exposure in the intestines could result in greater weight loss and whether tolerability would be improved compared with same/similar total daily once daily dosings. Administration of LIK066 three times daily did not result in better weight loss or tolerability [data on file] compared to bid dosing and therefore is not included in this study.

The eight active treatment regimens consist of four qd regimens and four bid regimens. The four qd regimens have been selected to cover one low dose (2.5 mg qd) at which some renal effect is present and no major gut effect is expected, two doses (10 mg qd and 50 mg qd) with sub-maximal/maximal renal and medium gut effect, and one qd dose (150 mg qd) with maximal renal and gut effects contributing to weight loss.

The four bid regimens have been selected to cover two low doses (2.5 mg and 5 mg bid) at which some renal effect is present and no major gut effect is expected, one dose (25 mg bid) with sub-maximal renal and medium gut effect, and one dose (50 mg bid) with maximal renal and gut effects contributing to weight loss.

Including both qd and bid dosing allows for thorough exploration of the LIK066 dose-response curve of a drug with a dual mechanism of action (ie gut and renal).

During Epoch 4, subjects will receive 25 mg qd or 35 mg qd LIK066. These doses provide sub-maximal/maximal renal effect and a moderate gut effect and are expected to provide for good maintenance of the weight loss achieved in Epoch 3.

The oral route of administration has been chosen, as in previous studies, to ensure that active drug is present in the gut lumen.

### **3.4 Rationale for choice of comparator**

A placebo group is a standard comparator in Phase 2 studies and is included to account for study effect and the lifestyle interventions described in [Section 3.1.1](#).

### **3.5 Purpose and timing of interim analyses/design adaptations**

Not applicable.

### **3.6 Risks and benefits**

The risk to subjects in this study will be minimized by compliance with the eligibility criteria and study procedures, and close clinical monitoring.

The potential risks of treatment with LIK066 are based on the observed safety and toxicology results of LIK066 in the pre-clinical studies, the Phase 1 clinical studies, and in published reports on SGLT2 inhibition in humans. LIK066 administration in repeated dose preclinical safety studies up to 13 weeks in duration was associated with GI side effects in dogs (diarrhea) and rats (adaptive change of cecum with hypertrophy/hyperplasia) which is consistent with SGLT1 inhibition. Other findings included reversible weight loss, increased calcium excretion (rats and dogs), increase in trabecular bone formation (rats), and renal changes (mineralization and hyperplasia in rats) likely due to increased calcium absorption in the intestines. Adaptive, reversible changes in liver glycogen were present in both rats and dogs which were associated with changes in glucose utilization. Reversible decreases in red blood cell count were present in both rats (doses  $\geq$  30 mg/kg) and dogs (doses  $\geq$  5 mg/kg). The no-observed-adverse-effect-level (NOAEL) was 5 mg/kg/day in rats and 0.5 mg/kg/day in dogs. In dogs, there was histological evidence of slight to moderate pyelonephritis in the mid and high dose groups, which was thought to be secondary to glucosuria and urinary catheterization for urine collection. No animals succumbed or required treatment for infection. Genotoxicity studies indicated that LIK066 is an aneugen ie a compound that produces aneuploidy (abnormal chromosome number) in dividing cells due to an effect on the spindle apparatus. There was no evidence in any assay that LIK066 directly damaged deoxyribonucleic acid (DNA). Aneogenicity is a threshold event and does not pose a risk for genotoxicity as long as exposure remains below the threshold. LIK066 is not genotoxic at the 150 mg clinical dose which results in an exposure  $\sim$ 23 times below the threshold for aneogenicity. The highest selected LIK066 dose will maintain at least a 10 times safety margin relative to the exposures associated with the NOAEL for micronucleus induction.

In embryo-fetal development studies conducted in rats and rabbits, no teratogenicity was observed in either species. Embryo-fetal toxicity or lethality in the absence of maternal toxicity was not observed in either species. In both species the embryo-fetal no-effect-level (NOEL) was higher than the maternal NOEL, indicating that maternal toxicity preceded any adverse fetal effects.

Based on the results of embryo-fetal development studies in rats and rabbits and a fertility study in rats, LIK066 is not anticipated to increase the risk of adverse developmental or reproductive outcomes in humans when administered at the maximum clinical dose of 150 mg. Women of child bearing potential must use basic contraception methods during the study (see [Section 4.2](#)). No such restriction exists for male subjects.

SGLT1 receptors are expressed in the heart, but their role is not well understood. In short-term studies (up to 12 weeks) of LIK066 150 mg qd in obese subjects, including subjects with T2DM, LIK066 was safe and well tolerated; GI side effects (ie flatulence, diarrhea, predominantly mild) were reported, but their incidence decreased over time in most subjects.

Publications on SGLT2 inhibition in subjects with T2DM treated with selective SGLT2 inhibitors reported higher incidences of urinary tract infections (UTIs) and genital mycotic infections compared with placebo ([Bailey et al 2010](#), [Nauck et al 2011](#), [Nyirjesy et al 2012](#)). SGLT2 inhibition may result in hypotension in elderly subjects, in subjects with low blood systolic pressure, or if on diuretics, ACEi, or ARB. Patients with T2DM treated with antidiabetic agents, especially with sulphonylurea or insulin, may be at an increased risk of hypoglycemia, which can be more pronounced with significant weight loss. In rare cases treatment with SGLT2 inhibitors may be complicated by ketoacidosis ([Rosenstock et al 2015](#)). However, this has not been seen to date in clinical studies with LIK066. In long-term clinical studies in patients with T2DM with CVD or at high risk for CVD, an increase in cases of lower limb amputation (primarily of the toe) has been observed with the SGLT-2 inhibitor canagliflozin ([Neal et al, 2017](#)). No lower limb amputations have been seen in LIK066 studies to date, but since this risk may constitute a possible class-effect, patients with a higher risk for amputation events should be instructed on routine preventative foot care and maintaining adequate hydration. The only preclinical/class safety issues which have been seen in clinical studies with LIK066 are the GI side effects and genital and UTIs. A detailed description of safety and tolerability in humans with LIK066 is found in the LIK066 investigator brochure (IB).

Hematology and biochemistry tests will be monitored at each study visit after randomization and study drug can be discontinued for clinically significant laboratory change or abnormality as per investigator's judgment. Detailed criteria for follow-up in case of a liver event are defined in [Section 7.3](#) and [Appendix 2](#). To prevent UTIs and genital infections, subjects will be instructed to pay attention to genital hygiene and have appropriate hydration. If UTI and/or genital infections occur, treatment will be initiated as appropriate at the investigator's discretion.

Benefits to participation in the study may include weight reduction and, potentially, improvement in some cardio-metabolic markers such as blood pressure (BP), lipids or blood glucose.

